Concurrent Therapies. Medication will be tapered to a minimum stable regimen by 6 weeks before implantation, in consultation with the most recent treating psychiatrist, as in our preliminary DBS OCD studies. The unmasked psychiatrist will prescribe during the blinded phase. Complete medication withdrawal is not required. Even if anti-OCD agents provide little benefit, withdrawal may expose severely ill individuals to an unacceptable risk of worsened OCD or comorbid depression and possibly of suicidality. Intermittent benzodiazepine treatment may be initiated during double masked DBS testing if needed for insomnia or extreme anxiety, but no other medication changes will be allowed. Patients may also continue

already established behavior therapy (of ≥4 months duration) during blinded study phases, but no new therapy may be started until masked testing is completed (3.5 months after implantation).

Measures

The instruments for Primary Efficacy Assessment are:

- Yale-Brown Obsessive-Compulsive Scale (YBOCS), a validated and reliable 40-item measure of the duration, severity, and functional impact of core OCD symptoms identified on an accompanying checklist (Goodman et al. 1989). Developed by investigators on this study, this is the most widely used measure of efficacy for OCD treatment studies.
- The clinician-rated Global Assessment of Functioning (GAF) (Hall 1995), and the Social and Occupational Function Assessment Scale (SOFAS), validated in psychiatric populations, will be used as global measures of psychiatric and functional status.

The instruments for Secondary Efficacy Assessment are:

- The Hamilton Depression Rating Scale (HDRS) will be administered at baseline and again at the 3 month time point. The Montgomery Asberg Depression Rating Scale (MADRS) will be used to quantify the severity of depressive symptoms at preoperative baseline and will serve as the principal, validated, change measure throughout the study (Montgomery & Asberg 1979). In addition, the Behavioral Activation for Depression Scale (BADS) will assess any change in the extent to which the patient is engaging in life activities (Kanter et al. 2006) and the Cognitive-Behavioral Avoidance Scale (CBAS) will quantify changes in cognitive and behavioral avoidance typical of depression (Ottenbreit & Dobson 2004).
- The Hamilton Anxiety Rating Scale (HARS) will be used as a validated measure of anxiety at baseline and throughout the study. (Hamilton 1959)

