- The clinician-rated Clinical Global Impression (CGI) Severity and Change scales (Hawley et al. 2002), and the patient-rated Patient Global Impression (PGI) scale will be used as validated global measures of illness severity and change.
- The two-item clinician-rated Clinical Global Impression – Exposure Therapy (GIT) will be used to assess a patient's ability to engage in behavioral/exposure therapy.

The quality of life measures are:

- The short form of the Quality of Life Enjoyment and Satisfaction Questionnaire (Q-LES-Q), a reliable and valid 16-item self-report of quality of life in 8 domains, widely used in treatment studies (Rapaport et al. 2005).
- The Range of Impaired Functioning Tool (LIFE-RIFT), a brief, validated, rater-administered scale measuring functioning in the home, work, school, interpersonal relationships, and recreation (Leon et al. 1999).

In the clinical interview the following safety measures will be administered:

- Adverse Events Questionnaire (AEQ) and accompanying Case Report Form (AEQ-CRF) will be used to assess potential major and minor adverse events in multiple domains, including psychiatric, neurological, and cognitive effects. The AEQ was based on one used in multiple DBS clinical trials, and includes cognitive and behavioral screening items used in the Cleveland Clinic DBS clinic for movement disorder patients. We have also added items for the adverse events observed in pilot DBS for OCD work across sites, plus further items covering other potential psychiatric and cognitive adverse events.
- A modified Young Mania Rating Scale (YMRS) (Young et al. 1978), this clinically validated scale will be used as a systematic screen for DBS-induced mania or hypomania. Although scores above 8 have been considered evidence of manic symptomatology in bipolar patients, the unmasked physician will use this scale and screening questions to assess whether *any* hypomanic symptoms require clinical intervention including DBS adjustment.

- The Columbia-Suicide Severity Rating Scale (C-SSRS) will be used to assess severity of and changes in suicidality. This scale provides a more specific classification system for the different levels of suicidality than any other measure (Posner 2007).
- Potential cognitive impairment will be assessed using the Mini-Mental State Examination (MMSE) (PAR 2007).

At the end of the formal consent session, the following measure will be administered by the Consent Monitor:

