Visit and Assessment Overview (Table, above). Diagnostic and Presurgical Evaluations are done in the screening phase, involving up to 2 visits. Two to four weeks after implantation, patients have Active or Sham Optimization outpatient visits. Visits will then be monthly (at a minimum) for three months to the end of masked testing. Visits during open continuation DBS occur at Months 6, 9, 12, 18 months and then every 6 months until the study ends. To reduce subject/family burden due to travel, ratings at 9, 18, and 24 months, and every 6 months thereafter, will be via telephone. Travel reimbursement will be equitable regardless of where patients live. A trained independent rater will give all efficacy measures during the masked phase. Clinicians familiar with adverse effects of DBS in OCD patients will administer the safety and tolerability measures.

Neuropsychological Testing will be obtained at presurgical baseline, and after 12 months of open continuation DBS. Tests will be administered by a highly experienced research neuropsychologist, [name] (Butler), who will assure that administration is standardized within study patients over time.

Comparison Neuropsychological Test Group. To obtain an estimate of practice effects and test-retest reliability coefficients in this patient population for data analysis (below), we will use the same cognitive battery and testing schedule in a comparison group of OCD patients (N=24, recruited 8 per site,) who would otherwise be candidates for surgery (i.e., meet study entry criteria) but have declined this treatment option. Given the likely effects of both OCD severity and comorbid depression on the cognitive assessments, these comparison patients will be group matched for baseline YBOCS and for depression severity on the MADRS. We chose these matching variables because we thought them the most important, and balancing groups on > 2 variables is problematic. Age corrections are incorporated into the normative data for the neuropsychological measures; thus matching for age is not critical for these neuropsychological measures. Potential group IQ differences are another concern. We do not expect these based on our pilot data, which found no significant differences across the three sites. If such differences emerge in this study, we would account for them in the analysis (discussion: Data Analysis, below).

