DBS Adjustment During the 3-Month Double-Masked Phase. After the optimization phase, adjustments for inadequate response (judged by the unmasked clinician) will involve adding an active cathode - either 0, 3, or potentially both, if both 1 and 2 are already active and negative. Intensity will be adjusted downwards as needed to observe the charge density limit based on measured impedance or to reduce intensity below any emergent side effects.

After the one week optimization phase, adjustments for treatment emergent adverse effects (determined by the unmasked clinician) will involve intensity reduction first, typically by 1-3V to below a detectability threshold, and, if this is insufficient, reducing the number of active cathodes by one, or changing to a different active cathode (from contact 0 to 1, e.g.) We will consider unilateral DBS, if necessary, to reduce adverse effects.

Open Continuation Phase. During open DBS, behavior therapy or medication changes will be allowed, and documented by the research team. During the open phase patients will be given a Medtronic Access Review device so that they can check stimulator battery status and DBS on or off, as an added safety measure. This device does not allow patients to change DBS amplitude, protecting against the risk of hypomania at higher currents.

Surgical Follow-up/INS Replacement. This will occur as needed, most often limited to INS replacement after battery depletion, which entails outpatient surgery under local anesthesia, expected every 10 - 24 months. All patients will be initially implanted with either the Activa PC or SC INSs. Replacement INSs may also be either Activa PCs or SCs. However, if the study psychiatrist feels they are good candidates, patients may choose to have their INSs replaced with Medtronic's Activa RC rechargeable battery and, in cases deemed appropriate by the surgeon, pocket adaptors. No Activa RC INSs will be used for initial implantation or, therefore, during the masked phase. This device requires the patient to regularly recharge the battery, thus the study psychiatrist will assess which patients will be best suited for this option. No INSs

will be replaced with Activa RCs during the blinded phase of the study.

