possibly due to the stimulation itself. Because hypomania is a risk of DBS treatment, albeit reversible in known cases to date, this trial will be limited to patients who have not had a manic episode in the preceding 3 years to reduce the risk of triggering a sustained manic episode in patients with bipolar illness. The main measure taken to reduce these risks will be maintaining close contact with patients and family/significant others. During the initial stimulator adjustments patients will be seen at least weekly and with additional telephone contact by the study nurse several times a week, allowing intervention in case of clinical deterioration. Patients, family and significant others will be told to notify the investigators immediately in the event of worsening of depressive symptoms, mood, anxiety, cognition, general level of functioning, or medical adverse events. The intervention may include DBS adjustment (by an unblended investigator, usually the PI), medication changes, or acute psychiatric hospitalization if clinically necessary. During the chronic open DBS phase, patients will be in telephone contact with the research team (study nurse) at least every 2 weeks, with monthly clinic visits. All of these contacts and clinic visits will, as much as possible, include family members or others in close touch with patients to maximize the monitoring information received. This will reduce the risk that a clinical deterioration would occur without intervention. In addition, the PI will be notified immediately if a patient obtains a score of 2 or more on the HDRS suicide item, or any increase in score on the YMRS, which could indicate hypomanic or manic symptoms.

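### The immediate PI alert for suicidality is keyed to the HDRS suicide item, but on the readable text the HDRS is given only once after implantation, at month 3

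*Protocol*

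**What the plan says.** In Management of Psychiatric Risks, Including Potential Suicidality, the protocol names close contact with patients and families as its main protection. It then adds a supplementary rule: "In addition, the PI will be notified immediately if a patient obtains a score of 2 or more on the HDRS suicide item". The rest of that sentence sets a parallel alert for any rise on the YMRS.

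The HDRS schedule is in Measures, under the secondary efficacy instruments: "The Hamilton Depression Rating Scale (HDRS) will be administered at baseline and again at the 3 month time point". The next sentence introduces the MADRS, which "will serve as the principal, validated, change measure throughout the study".

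The safety measures in the same section include the C-SSRS, which "will be used to assess severity of and changes in suicidality". No level of the C-SSRS is linked to notifying the PI.

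Visit and Assessment Overview sets the contact schedule. For the masked phase: "Visits will then be monthly (at a minimum) for three months to the end of masked testing". For the open phase: "Visits during open continuation DBS occur at Months 6, 9, 12, 18 months and then every 6 months until the study ends". It also assigns the safety scales: "Clinicians familiar with adverse effects of DBS in OCD patients will administer the safety and tolerability measures". That section points to a table which is not in the readable text.

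**The concern.** An alert that depends on a score can fire only when the scale is scored. The protocol fixes an immediate alert on one instrument and then schedules that instrument at a single point after surgery.

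The alert concerns a risk that the protocol itself treats as serious. Potential Risks reports suicide attempts and several suicides among patients with OCD waiting for surgery, and one suicide in another trial of DBS for OCD. It also warns that non-responders may carry a continuing suicide risk. The psychiatric-risk section lists device shutoff and battery depletion among possible causes of increased suicidality. The section on surgical follow-up expects battery replacement every 10 to 24 months, which falls in the open phase, where the alert is stated at no rating.

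At stake is whether a safety rule that the sponsor chose to write down works at the contacts where patients are actually seen.

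**Working it through.** There is no formula to check here. The check sets the sections side by side.

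**1. Where the HDRS appears.** It appears in two places: the Measures sentence that schedules it and the alert that relies on it. No other readable text schedules it.

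**2. How to read the schedule.** The Measures sentence does not say that the two time points are exclusive. But the neighbouring scales are described differently: the MADRS and the Hamilton anxiety scale both run throughout the study, while the HDRS alone gets two named time points. The natural reading is that it is not given elsewhere.

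**3. Where the alert can operate after implantation.**

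| Phase | Contacts stated in Visit and Assessment Overview | HDRS stated at |
|---|---|---|
| Optimization | Visits starting two to four weeks after implantation | none |
| Masked phase, monthly minimum | Months 1, 2, 3 | month 3, so 1 of 3 |
| Open phase to month 12 | Months 6, 9, 12 | 0 of 3 |
| Open phase after month 12 | Month 18, then every 6 months | none |

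The psychiatric-risk section describes denser contact in the open phase: calls at least every two weeks and monthly clinic visits. That changes how often patients are seen but not the result, because the HDRS is stated at none of those contacts either. The same holds in the masked phase if the weekly visits promised for initial adjustments extend into it. Larger denominators would add nothing to the one fact that matters: one stated HDRS rating after implantation.

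**4. Whether another rule fills the gap.**
- C-SSRS: a safety measure, with no notification level attached.
- Escape Criteria: these define active suicidality on the C-SSRS as an actual attempt with lethality of 3 or higher, or an interrupted attempt judged potentially serious. This is a separate score-based route, and it leads to exit from the masked arm. It acts at a far more severe point than a score of 2 on the HDRS item.
- YMRS alert: aimed at hypomania or mania. It does not depend on the HDRS and is unaffected.

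The HDRS rule is therefore the only stated score-based notification of the PI for suicidality.

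**The case against.** The strongest objection is the missing table. A visit table is the usual place to fix which scale is given when, and it may list more HDRS ratings. This limits certainty, but it does not remove the mismatch. Further HDRS ratings in the table would not fit the Measures sentence, so one sentence or the other would still need an edit.

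The second objection is that little is lost in practice, and much of it stands. The C-SSRS and the adverse events questionnaire, which covers psychiatric events, are safety measures given by clinicians who know DBS adverse effects. The PI monitors day-to-day safety and is usually the person adjusting stimulation. The nurse telephones several times a week during initial adjustments. Adjustment also continues afterwards, under "DBS Adjustment During the 3-Month Double-Masked Phase". Patients and families can reach the nurse and the PI at any hour.

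Three stronger readings might tempt a reader, and the documents support none of them:
- That suicidality goes unmonitored outside month 3. The safeguards just listed do not depend on the HDRS.
- That the HDRS item is the only route that starts from a suicidality score. The escape rule starts from C-SSRS ratings.
- That escapes or the masked comparison are affected. Escape is defined on the C-SSRS, and nothing in the text links the HDRS alert to the primary outcome.

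**Conclusion.** The point holds as a minor internal inconsistency: the alert and the schedule of the scale it depends on do not fit together. Its size is one stated HDRS rating after implantation, at month 3, and none in the open phase. The alert supplements other safeguards, so what is weakened is one added safety rule and not the monitoring as a whole.

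The conclusion rests on two assumptions: that the two named HDRS time points are meant as the full schedule, and that the unseen visit table does not add others. Confidence is medium for that reason. This is not detail that could be left to a statistical analysis plan, because the protocol itself fixes both the safety rule and the schedule.

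**What to change.** Either of two edits would do.

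- **Preferred.** In Management of Psychiatric Risks, tie the immediate PI notification to a stated C-SSRS ideation level, with the cut-off chosen by the clinical team. In Measures, state that the C-SSRS is given at every masked and open visit or telephone rating. It is already a clinical-interview safety measure, so the masked efficacy rater gains no work.
- **Alternative.** Keep the cut-off of 2 and state in Measures that the HDRS suicide item is also scored at each of those contacts. It should be scored by the clinician giving the safety measures. An independent rater gives all efficacy measures in the masked phase, so without that statement the task would fall to the masked rater.

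If the visit table already schedules more HDRS ratings, correct the Measures sentence to match it, and check that those ratings cover the open phase.

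The cost is about two sentences and no new visit. The downside is a short added rating at contacts that already take place; the protocol gives no duration for it, so its brevity is an assumption.
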